## 9.13 Treatment after End of Study

After the end of the study, each subject will be treated according to standard clinical practice. In order to support a subject's transition from the clinical trial, after care and medical oversight will be covered in the amount of \$250.00 per month for a total of up to 3 months. Payment will be made to the site to ensure appropriate medical oversight of the subject during titration and to cover costs for prescribed medication within the allotted total.

#### 10. STUDY PROCEDURES

Subjects will provide written informed consent before any study-related procedures are initiated, including the cessation of prohibited concomitant therapy.

For the timing of assessments and procedures throughout the study, refer to the schedule of events (Section 17.1). Throughout the study, every reasonable effort should be made by study personnel to follow the timing of assessments and procedures in the schedule of events for each subject. If a subject misses a study visit for any reason, the visit should be rescheduled as soon as possible, ideally within 2 days of the originally scheduled date.

## 10.1 Study Periods and Visits

## 10.1.1 Screening and Wash-out

## 10.1.1.1 Screening (Visit 1, Day -21 [± 2 days])

The subject must be screened within 21 days [ $\pm$  2 days] before enrollment in the study. The following procedures will be performed at Screening:

- 1. Obtain written informed consent/assent.
- 2. Perform a psychiatric evaluation Kiddie Schedule for Affective Disorders and Schizophrenia Present and Lifetime Version (K-SADS-PL).
- 3. Conduct the WASI-II brief IQ test (IQ should be > 79).
- 4. Conduct ADHD-RS-5 evaluation.
- 5. Conduct CGI-S evaluation.
- 6. Review inclusion/exclusion criteria.
- 7. Collect demographic information.
- 8. Record medical and medication history including confirmation from the sponsor that each subject has been determined to have disruptive mutations in genes within the GRM-network as determined by the presence of CNVs (GRM biomarker-positive subjects).
- 9. Perform a physical examination including vital signs (resting blood pressure, heart rate, and respiratory rate), weight, and height.
- 10. Collect blood and urine for clinical laboratory tests: hematology, serum chemistry, and urinalysis.
- 11. Perform 12-lead ECG.
- 12. Perform a serum pregnancy test (for females of childbearing potential only).
- 13. Perform urine drug test.
- 14. Conduct C-SSRS evaluation.
- 15. Access IWRS.
- 16. Assess and record concomitant medication and ongoing AEs.

If more than 23 days have elapsed between the Screening Visit and the Baseline Visit the following procedures must be repeated and the results available and reviewed prior to proceeding with the Baseline Visit:

- Collect blood and urine for clinical laboratory tests: hematology, serum chemistry, and urinalysis.
- Perform a serum pregnancy test (for females of childbearing potential only).
- Measure vital signs (resting blood pressure, heart rate, and respiratory rate) and weight.
- Perform 12-lead ECG.
- Perform urine drug test.

## 10.1.1.2 Wash-out Period

Caregivers will receive a telephone call no later than at Day -14 ( $\pm$  2 days) before the scheduled day of treatment initiation to confirm that stimulant and/or non-stimulant therapies for ADHD are being washed out.

The following details will be recorded:

- 1. Review inclusion/exclusion criteria.
- 2. Assess and record concomitant medication and newly occurring AEs since the last evaluation.

Subjects who do not require a washout call must still be contacted by phone prior to the Baseline visit being conducted.

## 10.1.2 Baseline (Visit 2, Day -1 $[\pm 2 \text{ days}]$ )

Subjects will attend a baseline visit (Day -1) on the day before starting study treatment (Day 1). Subjects who remain eligible for the study will be given blinded IP at the initial dose (100 mg twice daily) to begin treatment the following day (Day 1).

The following procedures will be performed at Visit 2:

- 1. Review inclusion/exclusion criteria.
- 2. The subject will be randomized to NFC-1 or placebo via IWRS.
- 3. Measure vital signs (resting blood pressure, heart rate, and respiratory rate) and weight.
- 4. Perform 12-lead ECG.
- 5. Perform a urine pregnancy test (for females of childbearing potential only).
- 6. Conduct ADHD-RS-5 evaluation.
- 7. Conduct CGI-S evaluation.
- 8. Conduct ASHS evaluation.
- 9. Conduct SCARED evaluation.
- 10. Conduct C-SSRS evaluation.
- 11. Access IWRS.
- 12. Dispense IP at initial dose level of 100 mg twice daily with instructions to begin taking the IP the following day.
- 13. Assess and record concomitant medication and newly occurring AEs since the last evaluation.

Version: Final Version v4.0 Page 30 of 58

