## 8.2 Study Entry Criteria

#### 8.2.1 Inclusion Criteria

A subject will be eligible for study participation if the subject meets all of the following criteria:

- 1. Subject is male or female,  $\geq 12$  to  $\leq 17$  years of age.
- 2. Subject has a body mass index in the range of  $\geq 15$  to  $\leq 35$  kg/m^2.
- 3. Subject has ADHD as defined by DSM-5 and ADHD-RS- $5 \ge 28$  at Baseline with or without conventional ADHD therapy.
- 4. Subject has an intelligence quotient (IQ) > 79, based on the Wechsler Abbreviated Scale of Intelligence, second edition (WASI-II).
- 5. Subject has been genotyped previously and determined to have disruptive mutations in genes within the GRM-network as determined by the presence of CNVs (GRM biomarker-positive subjects). The confirmation of a subject's positive status will be provided by the sponsor.
- 6. Subject is a non-smoker and/or has not used nicotine or nicotine-containing products on a weekly or more frequent basis for at least approximately 6 months.
- 7. Subject is judged to be in general good health, other than having ADHD, based on medical history, physical examination, vital signs measurements, laboratory safety tests, and the C-SSRS performed at the Screening Visit and/or prior to administration of IP.
- 8. Female subjects of reproductive potential will have a negative pregnancy test at Screening (serum) and prior to drug administration (urine). If sexually active, female subjects agree to use (and/or have her partner use) 2 acceptable methods of birth control beginning at least 2 weeks prior to administration of IP and throughout the study. Acceptable methods of

- birth control are abstinence or 2 of the following: intrauterine device, diaphragm, spermicides, cervical cap, contraceptive sponge, and condoms.
- 9. Subject has no clinically significant abnormality on ECG performed at the Screening Visit and/or prior to administration of IP such as serious arrhythmia, bradycardia, tachycardia, cardiac conduction problems, or other abnormalities deemed to be a potential safety issue.
- 10. Parent/legal guardian and subject understand the study procedures and agree to the subject's participation in the study as indicated by parental/legal guardian signature on the subject informed consent form and subject signature on the assent form.

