## 8.4 Subject Replacement Criteria

Once randomized, subjects who discontinue from the study will not be replaced.

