3 OVERALL STUDY DESIGN AND PLAN

This is a randomized, double-blind, placebo-controlled, parallel-group phase 2 study of adolescents to compare the safety and efficacy of NFC-1 with that of placebo. Approximately 90 male and female subjects will receive randomized treatment with NFC-1 or placebo to obtain 80 subjects that complete the study as planned. Subjects must be ≥ 12 to ≤ 17 years of age and have ADHD as defined by the Diagnostic and Statistical Manual of Mental Disorders, 5th edition (DSM-5) and an ADHD-RS-5 ≥ 28 at Baseline. The study will take place in approximately 25 sites in the United States.

The overall maximum study duration for an individual subject is expected to be 70 days with maximum treatment duration of 42 days. As per the schedule of events below (Table 1), subjects will be randomly assigned in a 1:1 ratio to receive either NFC-1 or placebo on Day -1 and will start taking investigational product (IP) at a dose of 100 mg twice daily on Day 1. Dosing will be optimized to 100 mg, 200 mg, or 400 mg twice daily as appropriate, over the 4 weeks of treatment (dose optimization phase), based on clinical response and tolerability. If the subject tolerates their final optimized dose well, the dose will be maintained for an additional 2 weeks (dose maintenance phase) when the primary assessments of efficacy and tolerability will be performed. A follow-up telephone call will be performed 7 days after the last visit.

Table 1. Schedule of Events

		Washand	Wash-out Treatment Period						7-day	
	Screening	Call	Baseline	Dose Optimization				Dose Maintenance		Follow-up Call ^a
Visit	1	No Visit	2	3	4	5	6	7	8/ET	No Visit
Assessment Day	-21	-14	-1	7	14	21	28	35	42	49
Visit Window	± 2 days	± 2 days	± 2 days	± 2 days	± 2 days	± 2 days	± 2 days	± 2 days	± 2 days	+ 5 days
Informed consent/ assent ^b	~									
Psychiatric evaluation (K-SADS-PL)	✓									
WASI-II (brief IQ test)	V									
Inclusion/exclusion criteria	~	✓ (review)	✓ (review)							
Demographics	V									
Randomization			✓							
Medical and medication history ^c	~									
Physical examination	V				3				✓	
Vital signs (resting blood pressure, heart rate, and respiratory rate)	~		~	~	~	~	~	~	~	
Height (calibrated stadiometer)	√				_				~	
Weight (calibrated scale)	V		✓	V	✓	V	✓	✓	✓	
Clinical laboratory test	V		✓	✓	✓	✓	✓	✓	✓	
12-lead ECG	~		✓	~	~	~	✓	~	~	
Serum pregnancy test (females of childbearing potential)	√									

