5 ANALYSIS POPULATIONS

The following analysis populations are planned for this study:

- Safety Population (SAFETY): The Safety Population includes all subjects who are randomized into the study and receive any amount of Investigational Product (IP).
- **Intent-To-Treat Population (ITT):** The ITT Population includes all subjects who are randomized into the study.
- **Per-Protocol Population (PP):** The PP Population includes all randomized subjects who do not have any significant protocol deviations defined as a major protocol deviation. Major protocol deviations are listed in section 7 (below). Membership in the PP population will be determined by a blinded review of patient data prior to database lock.

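### Protocol 10.1.2 lists randomization before the Baseline ADHD-RS-5 that alone decides inclusion criterion 3, in conflict with 9.3 and 9.5

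*Protocol*

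**What the plan says.** Protocol 10.1.2 gives a numbered list of 13 procedures for Visit 2. Item 1 is the review of entry criteria. Item 2 is "The subject will be randomized to NFC-1 or placebo via IWRS". ECG is item 4, the urine pregnancy test item 5, and item 6 is "Conduct ADHD-RS-5 evaluation". Access to the IWRS appears separately as item 11, and dispensing is item 12. The introduction to the same section says "Subjects who remain eligible for the study will be given blinded IP at the initial dose (100 mg twice daily"), with dosing to start the next day.

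Inclusion criterion 3 (Protocol 8.2.1) requires an ADHD-RS-5 of 28 or more "at Baseline with or without conventional ADHD therapy". SAP section 3 repeats the threshold as "an ADHD-RS-5 ≥ 28 at Baseline".

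Protocol 9.3 says that it is eligible subjects who are randomized, and 9.5 says that it is subjects meeting the entry criteria. Section 9.5 also bars randomizing any subject twice.

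On what follows randomization, Protocol 8.4 states "Once randomized, subjects who discontinue from the study will not be replaced", and SAP section 5 states "The ITT Population includes all subjects who are randomized into the study". SAP 8.1 runs the primary ANCOVA on the ITT set and carries forward the last treated ADHD-RS-5 value for subjects who stop before Visit 8.

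**The concern.** The only criteria review in the Visit 2 list stands before the measurement that settles one of the criteria. The Screening score cannot take its place: criterion 3 names Baseline, and ADHD medication may be washed out between the two visits. The Screening list (10.1.1.1) has the ADHD-RS-5 at item 4 and the criteria review at item 6. Visit 2 reverses that order at the visit where the score counts.

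Randomizing too early cannot be undone. Before randomization, a subject scoring below 28 is a screen failure and costs the trial nothing statistically. After randomization, the same subject is counted in the primary analysis set, uses up one of about 90 places, and cannot be replaced or randomized again.

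**Working it through.** **Step 1: which Visit 2 checks must come before randomization.**

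| Criterion (Protocol 8.2.1) | Timing the criterion requires | Item in 10.1.2 | Met by the listed order? |
|---|---|---|---|
| 3, ADHD-RS-5 of 28 or more | At Baseline | 6 | No: undecided when item 2 is reached |
| 8, urine pregnancy test | Before drug administration | 5 | Yes: first dose is the day after Visit 2 |
| 9, ECG | Screening and/or before investigational product | 4 | Yes, for the same reason |

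Only criterion 3 rests on the Visit 2 value alone. The urine test and ECG are supporting points.

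**Step 2: what happens to a subject randomized at item 2 who scores below 28 at item 6.**

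- ITT set: included, because every randomized subject is (SAP 5; Protocol 13.3).
- Replacement: none (Protocol 8.4).
- Second randomization: barred (Protocol 9.5).
- Dosing: should not occur, because 10.1.2 gives product only to subjects who remain eligible. The subject is then in ITT but not in the Safety Population.
- Primary analysis: an undosed subject has no treated value to carry forward (SAP 8.1), and SAP 6.2 allows no other imputation of the endpoint beyond the item-level rule in 6.3. The SAP does not say how such a subject enters the ANCOVA.

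**Step 3: the plan's power figure.** Inputs are a standardized effect of 0.7, two-tailed alpha of 0.05, 90 enrolled and 80 completing (Protocol 13.2), and about 45 per arm (Protocol 7.1). With n per arm, the normal approximation is

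power = Φ(0.7 × √(n/2) − 1.960).

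- n = 45 (all randomized): Φ(3.320 − 1.960) = Φ(1.360) = 91.3%. The noncentral t gives 90.7%.
- n = 40 (completers): Φ(3.130 − 1.960) = Φ(1.170) = 87.9%. The noncentral t gives 87.1%.

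The stated power of approximately 90% is therefore reproduced on the 90 randomized, which is also the set that an ITT analysis with LOCF uses.

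**Step 4: possible loss.** Let k be the number randomized, then found ineligible, contributing no data and split evenly between arms. The documents give no value for k, so the range is an assumption. Then n = (90 − k)/2.

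| k (assumed) | n per arm | Power, normal | Power, noncentral t | Loss (normal) |
|---|---|---|---|---|
| 0 | 45 | 91.3% | 90.7% | 0 |
| 4 | 43 | Φ(3.246 − 1.960) = 90.1% | 89.4% | about 1.2 points |
| 8 | 41 | Φ(3.169 − 1.960) = 88.7% | 87.9% | about 2.6 points |

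**The case against.** The strongest reply is that position in a list is not an instruction about sequence. Section 10.1.2 says only that these procedures take place at Visit 2. Section 10 refers timing to the schedule of events, which gives no order within a visit. Other lists are plainly not chronological: at Visits 3 to 6, dispensing (item 9) precedes return of unused product (item 10), and at Screening the criteria review (item 6) precedes the laboratory tests and ECG. Within Visit 2 itself, IWRS access is item 11, which fits randomization being done there, after all the assessments. Sections 9.3 and 9.5 already restrict randomization to eligible subjects, so a site that randomized first would breach them. The IWRS user manual mentioned in 9.4.1 is not available here, and an eligibility check may already be built in.

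All of this stands as a limit on the finding. It rules out reading the list as a decision to randomize before eligibility is known. It does not remove the conflict: no passage tells sites to finish the Visit 2 assessments first, and having randomization at item 2 and IWRS access at item 11 also allows the literal reading that allocation comes first and kits are assigned later.

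**Conclusion.** The point holds as an inconsistency between the visit procedure in 10.1.2 and the rule in 9.3 and 9.5. If followed in number order, it can cause an enrolment error that cannot be reversed. Its size is unknown. On the 90 randomized, the power loss is about 1 to 3 points if 4 to 8 subjects (assumed) contribute no data, and zero if none fail.

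A reader might infer four stronger things that the documents do not support:

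- **That the ECG and urine pregnancy test are equally misplaced.** Their criteria are met by checks before dosing, which the listed order provides.
- **That ineligible subjects would be treated and dilute the effect.** This would need a second breach, since 10.1.2 gives product only to those who remain eligible.
- **That power falls to 83–85%.** Taking 40 completers per arm down to 38 or 36 gives noncentral t power of 85.4% or 83.4%. But the 40 is already net of the 10 planned losses, the primary analysis is ITT with LOCF, and the 5–10% failure rate behind those counts appears nowhere in the documents.
- **That scoring Baseline after allocation biases the comparison.** Protocol 9.6 blinds subjects, investigators and study personnel to assignment, and all subjects start at the 100 mg level or matching placebo, so the IWRS call does not reveal the arm.

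**What to change.** In Protocol 10.1.2, move randomization to follow completion and review of the Visit 2 eligibility assessments, next to the IWRS access step (now item 11), and refer to 9.3 and 9.5 so that the three sections agree. Have the IWRS require confirmation of eligibility, including entry of the Baseline ADHD-RS-5 total, before it releases a randomization number. If the system already does this, say so in 9.4.1.

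As a companion change, one sentence in SAP 8.1 should state how the primary analysis treats a randomized subject with no post-baseline ADHD-RS-5.

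The cost is one reordered list, one IWRS entry check and one sentence. The sample size, endpoint and analysis model do not change.

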#### 10.1.3 Double-blind Treatment Period

The double-blind treatment period will comprise a dose optimization phase of 28 days and a subsequent dose maintenance phase of 14 days.

# 10.1.3.1 Dose Optimization Phase (Visit 3, Day 7 [± 2 days], Visit 4, Day 14 [± 2 days], Visit 5, Day 21 [± 2 days], and Visit 6, Day 28 [± 2 days])

Subjects will take 100 mg NFC-1 or placebo twice daily from Study Day 1. During the 4-week dose-optimization phase, subjects will be administered 100 mg, 200 mg, or 400 mg IP twice daily based on dose assessments performed by the investigator.

Subjects will attend a visit for evaluation by the investigator on the last day of each week of treatment during the optimization phase. Subjects will undergo the same evaluations at the end of each of the 4 weeks of the dose-optimization phase. During these visits, the investigator will assess the tolerability and efficacy of the subject's current IP dose, and categorize their response as intolerable, ineffective, or acceptable. Based on this categorization, the subjects will be dispensed the next appropriate dose of the IP, to begin taking at the next scheduled dosing timepoint (see Section 9.9 for the definition of the dose adjustment criteria).

The following procedures will be performed at Visit 3 (Day 7 [ $\pm$  2 days]), Visit 4 (Day 14 [ $\pm$  2 days]), Visit 5 (Day 21 [ $\pm$  2 days]), and Visit 6 (Day 28 [ $\pm$  2 days]):

- 1. Measure vital signs (resting blood pressure, heart rate, and respiratory rate) and weight.
- 2. Collect blood and urine for clinical laboratory tests: hematology, serum chemistry, and urinalysis (at Visit 3 only).
- 3. Perform 12-lead ECG.
- 4. Perform a urine pregnancy test (for females of childbearing potential only).
- 5. Conduct ADHD-RS-5 evaluation.
- 6. Conduct CGI-I evaluation.
- 7. Conduct C-SSRS evaluation.
- 8. Access IWRS.
- 9. Conduct dose assessment and dispense the IP at the appropriate dose level, with instructions to begin taking the provided IP at the next scheduled dosing timepoint.
- 10. Subject returns unused IP.
- 11. Assess subject compliance using returned IP.
- 12. Assess and record concomitant medication and newly occurring AEs since the last evaluation.

# 10.1.3.2 Dose Maintenance Phase (Visit 7, Day 35 [± 2 days], Visit 8, Day 42 [± 2 days], or Early Termination) Evaluation

At Day 35 and Day 42 or ET of the study, the following procedures will be performed:

- 1. Perform a physical examination and measure height (at Visit 8/ET only).
- 2. Measure vital signs (resting blood pressure, heart rate, and respiratory rate) and weight.
- 3. Collect blood and urine for clinical laboratory tests: hematology, serum chemistry, and urinalysis (at Visit 8/ET only).
- 4. Perform 12-lead ECG.
- 5. Perform a urine pregnancy test (for females of childbearing potential only).

- 6. Conduct ADHD-RS-5 evaluation.
- 7. Conduct CGI-S evaluation (at Visit 8/ET only).
- 8. Conduct CGI-I evaluation.
- 9. Conduct ASHS evaluation (at Visit 8/ET only).
- 10. Conduct SCARED evaluation (at Visit 8/ET only).
- 11. Conduct C-SSRS evaluation.
- 12. Access IWRS.
- 13. Subject returns unused IP.
- 14. Assess subject compliance using returned IP.
- 15. Assess and record concomitant medication and newly occurring AEs since the last evaluation.

## 10.1.4 7-day Follow-up Call

At Day 49 (+ 5 days), caregivers will receive a telephone call to assess and record concomitant medication and newly occurring AEs since the last evaluation.

## 10.2 Study Duration

The overall study duration is expected to be 70 days (including up to 21 days of screening inclusive of a maximum 14 days of wash-out, approximately 42 days of treatment, and a follow-up period of approximately 7 days).

The planned sequence and maximum duration of the study periods will be as follows:

- 1. Screening period: approximately 21 days.
- 2. Wash-out period: if applicable, up to 14 days.
- 3. Dose optimization phase: 28 days.
- 4. Dose maintenance phase: 14 days.
- 5. Follow-up: 7 days (+5 days) after the last dose of IP.

The maximum study duration for each subject is approximately 70 days.

The maximum treatment duration for each subject is 42 days.

## 10.3 Assessments

## 10.3.1 Screening

#### 10.3.1.1 Kiddie Schedule for Affective Disorders and Schizophrenia – Present and Lifetime

The K-SADS-PL is a semi-structured diagnostic interview designed to assess current and past episodes of psychopathology in children and adolescents according to Diagnostic and Statistical Manual of Mental Disorders, 3rd Edition, Revised (DSM-III-R) and Diagnostic and Statistical Manual of Mental Disorders, 4th Edition (DSM-IV) criteria. Probes and objective criteria are provided to rate individual symptoms.

The primary diagnoses assessed with the K-SADS-PL include, but are not limited to: major depression, dysthymia, mania, bipolar disorders, schizoaffective disorders, panic disorder, agoraphobia, separation anxiety disorder, avoidant disorder of childhood and adolescence, simple phobia, social phobia, overanxious disorder, generalized anxiety, obsessive compulsive disorder, ADHD, conduct disorder, and oppositional defiant disorder.

The K-SADS-PL will be administered by the investigator, by interviewing the parent or caregiver, the child, and finally achieving summary ratings, which include all sources of information (parent or legal caregiver, child, school, chart, and other).

*Time of administration: 90 minutes* 

## 10.3.1.2 Wechsler Abbreviated Scale of Intelligence

The WASI-II is administered by the investigator. It comprises a 4 sub-test form (vocabulary, similarities, block design, matrix reasoning) and yields 3 scales:

- Full Scale IQ-4 score: estimate of generalized cognitive ability.
- Verbal Comprehension Index score: measure of crystallized abilities.
- Perceptual Reasoning Index score: measure of nonverbal fluid abilities and visuomotor/coordination skills.

Time of administration: 30 minutes

